## ABBREVIATIONS AND DEFINITIONS OF TERMS

Abbreviation	Definition
ACL	Anterior cruciate ligament
ACLR	Anterior cruciate ligament reconstruction
CAR	Central activation ratio
HST	Heelstrike transient
LMV	Local muscle vibration
OA	Osteoarthritis
vGRF	Vertical ground reaction force
WBV	Whole body vibration

## PROTOCOL SYNOPSIS

Study Title	Vibratory Stimuli: A Novel Rehabilitation Method for Preventing Post-Traumatic Knee Osteoarthritis
Funder	US Department of Defense
Clinical Phase	Phase II
Study Rationale	
Anterior cruciate ligament injury and reconstruction surgery (ACLR) dramatically increase the risk of developing knee osteoarthritis (OA). Individuals with ACLR possess deficits in quadriceps muscle function and proprioception (joint position sense) that alter knee joint loading during tasks such as walking in manners that contribute to development of knee OA. Vibratory stimuli enhance quadriceps function and proprioception and may, therefore, reduce the risk of knee OA. The purposes of this study are to 1) evaluate and compare the effects of whole body vibration (WBV) and local muscle vibration (LMV) on quadriceps function, knee joint proprioception, and walking gait biomechanics in individuals with ACLR and 2) identify characteristics that determine the efficacy of WBV and LMV for improving quadriceps function, knee joint proprioception, and walking gait biomechanics in individuals with ACLR.

Study Objective(s)	
Primary
 
 
• To determine the effects of WBV and LMV on quadriceps function, proprioception, and gait biomechanics in individuals ACLR
 
• To compare the effects of WBV and LMV on quadriceps function, proprioception, and gait biomechanics in individuals ACLR
 
• To identify factors that predict the effects of LMV and WBV on quadriceps function, proprioception, and gait biomechanics in individuals ACLR
 

Test Article(s)	WBV or LMV delivered at a frequency of 30Hz and intensity of 2g
Study Design	
This preclinical investigation will utilize a single-blind randomized controlled experimental design whereby 75 individuals with primary unilateral ACLR will be randomly assigned to WBV, LMV, and Control groups. Stratified randomization into 3 groups of equal size (<math>n = 25</math>) will be performed using a computer generated randomization algorithm to ensure stratification with respect to age and time since ACLR.

Subject Population	Inclusion Criteria
key criteria for Inclusion and Exclusion:	
 
1. Subjects age 18-35
 

---

2. Undergone primary unilateral ACLR within 6 months to 5 years of participation
3. Knee Injury and Osteoarthritis Outcome Score (KOOS) self-report survey Pain subscale score > 53.1 and Symptom subscale score > 44.9
4. Cleared by physician to resume physical activity, and currently physical active at least 20 minutes 3x per week
5. Quadriceps central activation ratio < 95%

Exclusion Criteria

6. History of ACL graft rupture
7. History of neurological disorder
8. History of musculoskeletal injury to either leg within the 6 months prior to participation
9. Pregnant or planning to become pregnant

---

Number Of Subjects	75
Study Duration	Each subject's participation will last approximately 3 hours and 45 minutes over approximately 2 weeks.  The entire study is expected to last 3 years.
Study Phases	(1) Screening : screening for eligibility and obtaining consent and (2) Intervention : study intervention/experimental treatment. Phase 2 will involve 2 testing sessions separated by approximately 1 week.
Screening	
Study Treatment	
Follow-Up	
Efficacy Evaluations	
 
1. Gait biomechanics (vertical ground reaction force linear and instantaneous loading rates, peak internal knee extension moment, peak internal knee valgus moment)
 
2. Somatosensory function (knee joint position sense error)
 
3. Quadriceps function (isometric peak torque)
 

Statistical And Analytic Plan	Pre-Post change scores for each of the primary outcomes will be compared between groups via one-way ANCOVA
DATA AND SAFETY MONITORING PLAN	[name] from the UNC-Chapel Hill Department of Orthopaedics will serve as the Research Monitor for this investigation. The PI will provide the Research Monitor a summary report during each quarter of the funding period that details information detailing enrollment, verification of informed consent, and adverse event documentation. The Research Monitor's primary responsibilities relate to the proper conduct of the investigation and the welfare of the subjects who are involved. As such, [name] will have the authority to suspend research associated with the project in the event of violations of study protocol.

---

[figure not shown]
# 1 BACKGROUND AND RATIONALE

## 1.1 Introduction

Osteoarthritis (OA) is the most common cause of medical discharge from military service during peacetime and the second most prevalent cause during armed conflict, ranking it as one of the largest military “force subtractors”. Traumatic knee injuries are of particular concern, as they almost universally result in post-traumatic OA in military personnel. Knee injuries comprise 19% of all injuries sustained during military training and 15% of all non-combat injuries during deployment. Additionally, knee injuries are the third most prevalent type of injury leading to battlefield evacuation, and Rivera et al. reported that 100% of knee injuries sustained during combat resulted in OA.

Anterior cruciate ligament (ACL) injury dramatically increases the risk of developing knee OA. ACL injury also accelerates knee OA development, as radiographic evidence of OA has been identified as early as 5 years following injury. While surgical reconstruction (ACLR) is the standard of treatment and improves joint stability, ACLR does not reduce the risk of developing knee OA. Therefore, *ACLR represents an ideal model for evaluating novel rehabilitation techniques for preventing development of post-traumatic knee OA.*

Impulsive/high rate joint loading contributes to the development of knee OA. Quadriceps dysfunction/weakness is a highly common, lingering complication associated with ACLR and other traumatic knee injuries that is caused by a neuromuscular phenomenon known as arthrogenic muscle inhibition (AMI). Because the quadriceps functions as a shock absorber in the early stance phase during walking and running gait, quadriceps dysfunction results in impulsive loading of the knee joint as evidenced by higher loading rates. Given the repetitive nature of gait and its integral role in human locomotion, this impulsive loading contributes to development of OA. Recent evidence suggests that quadriceps dysfunction associated with ACLR results in joint space narrowing, a radiographic indicator of knee OA. Individuals with traumatic knee injuries also display sensory/proprioceptive deficits which magnify quadriceps dysfunction and contribute to impulsive loading. As such, treatments that improve quadriceps function and proprioception may reduce the risk of developing post-traumatic knee OA (Figure 1).

**Figure 1:** Knee injuries lead to proprioceptive deficits and quadriceps dysfunction. These factors alter gait biomechanics in manners which contribute to development of post-traumatic knee OA. Vibratory stimuli may prevent these negative effects, thus mitigating the risk of post-traumatic knee OA.

## 1.2 Name and Description of Investigational Product or Intervention

Whole Body Vibration (Power Plate pro5)

Local Muscle Vibration (prototype stimulator – IDE granted by UNC-Chapel Hill Biomedical Institutional Review Board)

## 1.3 Non-Clinical and Clinical Study Findings

Quadriceps strengthening is an inherent component of rehabilitation of ACLR and other traumatic knee injuries, but is commonly ineffective due to the fact that the underlying neural deficiencies (i.e. AMI) are not addressed by conventional approaches. However, both direct (local muscle vibration - LMV) and indirect (whole body vibration - WBV) vibratory stimuli enhance quadriceps function in individuals with non-pathological knees, and may minimize the negative effects of AMI. We demonstrated that LMV enhances quadriceps function in healthy individuals, and that both WBV and LMV produce

equivalent improvements in quadriceps function following experimental knee joint effusion (i.e. simulated knee trauma) in healthy individuals. Vibratory stimuli also improve proprioception, and we demonstrated that improving knee proprioception decreases impulsive loading during walking gait in individuals diagnosed with knee OA. *These findings suggest that vibratory stimuli may improve quadriceps function, proprioception, and gait biomechanics (e.g. impulsive loading) following traumatic knee injuries, potentially reducing the risk of developing knee OA.*

Our preliminary data and findings reported by other researchers support our hypothesis that vibratory stimuli may enhance rehabilitation of traumatic knee injuries. These studies indicate that incorporation of vibratory stimuli into ACLR rehabilitation improves postural stability, quadriceps strength, and proprioception. Additionally, a recent animal model demonstrated that WBV minimized articular cartilage loss in rats with knee OA caused by ACL transection. However, *the effects of vibratory stimuli on factors linked to the development of post-traumatic knee OA have yet to be investigated.*

Clinical application of WBV may be limited, as these devices require a fixed location, permit limited types of rehabilitation exercises due to the restricted space of the device (~5 ft), and may be cost-prohibitive (as much as \$10,000). However, LMV can be integrated into a portable, cost-effective device (~\$250) for use in a variety of rehabilitation tasks and settings. LMV may also be more effective, as it is applied directly to the quadriceps, thus it is less susceptible to damping of the vibratory stimulus as it passes through the lower extremity such as occurs with WBV. However, *it is unclear if WBV and LMV have similar effects on quadriceps function, proprioception, and gait biomechanics in individuals with traumatic knee injuries.*

The results of this investigation will provide “proof of concept” regarding the utility of WBV and LMV for prevention and management of knee OA, and will advance our understanding of the development and progression of this disease. Traditional rehabilitation and treatment methods have been only moderately effective due to the fact that AMI limits the efficacy of quadriceps strengthening by preventing adequate activation. Therefore, the results of this investigation may promote the development of improvements in patient care by supporting a shift in the treatment of knee pathologies (i.e. by demonstrating that AMI should be addressed before attempting to strengthen the quadriceps to enhance traditional rehabilitation). As knee OA adversely affects quality of life, the improved ability to treat and prevent knee OA resulting from this investigation would lead to improvements in quality of life. This information would also inform the development of a larger, long-term clinical trial to evaluate these effects on the long-term health and clinical outcomes in individuals who are afflicted with knee OA or are at heightened risk for development of post-traumatic knee OA. These outcomes would have a direct impact on the substantial burden of knee OA on the US health care system.

Exercise in general, including rehabilitation exercise, carries the risk of injury, pain, and soreness/discomfort. However, the tasks subjects will be asked to perform in this investigation are common to activities of daily living and rehabilitative exercise (i.e. quadriceps contractions, squatting, and walking), and strength training, and do not present increased risk of adverse events compared to these same risks when these activities are performed outside the laboratory setting (i.e. rare). The risk of subjects experiencing mild discomfort for a brief period of time (less than 1 second) during the electrical stimulation used for the Quadriceps Function Assessment is very common. However, this discomfort will immediately cease, and subjects will be familiarized with the electrical stimulation before

[figure not shown]
[figure not shown]
the testing procedure begins. Exposure to vibration may infrequently cause itching in the lower extremity and dizziness, both of which typically subside within minutes following exposure.

#### 1.4 Relevant Literature and Data

We have conducted a series of investigations that support the rationale for the proposed investigation and demonstrate our ability to conduct the proposed RESEARCH STRATEGY. Each study is described below.

[figure not shown]
1. **LMV enhances quadriceps function several minutes following application.** We evaluated the effects of LMV on quadriceps activity in healthy individuals with non-pathological knees (n=22). Quadriceps activity (electromyographic amplitude) was measured during maximal isometric contractions prior to and immediately, 5, 15, and 30 minutes following LMV or a Control condition (no vibration). A custom-built device identical to what we have proposed was used to deliver the LMV stimulus. LMV enhanced quadriceps activity, and this effect persisted for several minutes following application (Figure 2). *These findings support our hypothesis that LMV enhances quadriceps function for a sustained period of time.* It is likely that these healthy individuals were subject to a “ceiling effect” regarding improvements in maximal quadriceps activity. This suggests that LMV has a robust neuromuscular effect, thus we anticipate that individuals with knee pathologies who possess deficits in quadriceps function (e.g. ACLR) will realize larger improvements in quadriceps function compared to the healthy individuals in this preliminary study.

2. **WBV and LMV enhance quadriceps function similarly in individuals with simulated knee trauma.** We evaluated the effects of WBV and LMV on quadriceps function in healthy individuals with simulated knee trauma (n=43). The underlying cause of quadriceps dysfunction, AMI, is attributable to sensory information that signals pathology including pain, inflammation, swelling, and damage to mechanoreceptors. AMI can also be induced experimentally by injecting saline into the knee joint which mimics the effects of swelling/effusion. Quadriceps function was assessed via the central activation ratio (CAR). CAR quantifies an individual’s ability to voluntarily activate a muscle, and is an indicator of AMI. A detailed description of this method is provided in the RESEARCH STRATEGY below. Following pre-test measures, 60mL of saline was injected into the knee joint space to induce AMI. Subjects were then exposed to WBV, LMV, or no vibration (Control), and quadriceps function was reassessed post-intervention. The interventions and methods for assessing quadriceps function utilized in this preliminary study are identical to those proposed in the RESEARCH STRATEGY. CAR improved significantly with WBV (+8.3%) and LMV (+5.9%), but not in the Control group (+0.7%). While both forms of vibration improved quadriceps function, this improvement did not differ between LMV and WBV. Additionally, subjects who experienced the greatest inhibitory effects of effusion displayed the greatest improvements in quadriceps function with vibratory stimuli. *These findings support our hypothesis that WBV and LMV may enhance quadriceps function similarly in individuals with knee pathology.* We

anticipate that individuals with “real” knee pathologies (as opposed to the acute, simulated trauma in this preliminary investigation) will realize substantially larger improvements in quadriceps function due to the chronic nature of their quadriceps dysfunction.

3. **Treatment modalities that improve proprioception may reduce impulsive loading.** We evaluated the effects of stochastic resonance electrical stimulation (SR) on proprioception and gait biomechanics in individuals with knee OA (n=52). Impulsive loading was quantified from the loading rates of the peak vertical ground reaction force (vGRF) and heel strike transient (HST). The HST is a rapid, transient rise in the vGRF which occurs shortly following ground contact during gait that is indicative of impulsive loading. SR improved proprioception and altered gait biomechanics in manners that may slow knee OA progression. Specifically, SR increased the knee flexion angle at ground contact, decreased quadriceps/hamstring coactivation, and decreased impulsive loading (Figure 4). *These findings demonstrate that modalities that improve proprioception potentially reduce impulsive loading.* We anticipate that WBV and LMV will both improve proprioception in individuals who have undergone ACLR, thus altering gait biomechanics in manners that would reduce the risk of developing knee OA.

**Figure 4:** SR improved knee proprioception and reduced impulsive loading as evidenced by significant\*decreases in the loading rates (Body Weight/s) of the heel strike transient (HST) and peak vertical ground reaction force (vGRF) compared to the Control/no SR condition.

[figure not shown]
## 2 STUDY OBJECTIVE

The long-term objective of this line of research is to improve rehabilitation of traumatic knee injuries and prevent post-traumatic knee OA. The objectives of this proposal are to 1) determine the acute effects of WBV and LMV on quadriceps function, proprioception, and gait biomechanics in individuals who have experienced traumatic knee injury (ACLR); 2) compare the efficacy of LMV and WBV for these purposes; and 3) identify factors which predict the efficacy of these modalities.

## 3 INVESTIGATIONAL PLAN (brief overview)

### 3.1 Study Design

This preclinical investigation will utilize a single-blind randomized controlled experimental design whereby 75 individuals who have undergone ACLR will be randomly assigned to WBV, LMV, and Control groups (Figure 5). This convenience sample will include individuals recruited from two local orthopaedic clinics (UNC Department of Orthopaedics and Triangle Orthopaedic Associates), local rehabilitation clinics, and the University population, as well as veterans recruited from the Veterans Affairs Medical Center in nearby Durham, NC. Quadriceps function, proprioception, and walking gait biomechanics will be assessed prior to and following vibratory treatments (LMV or WBV) or a Control intervention. The WBV and LMV groups will

receive a single session of vibratory stimuli which we previously demonstrated to enhance quadriceps function. The Control group will perform identical procedures, but no vibratory stimulus will be applied.

### **3.2 Allocation to Treatment Groups and Blinding (if applicable)**

Stratified randomization into 3 groups of equal size (n = 25) will be performed using a computer generated randomization algorithm. This algorithm will ensure stratification with respect to age and time since ACLR.

### **3.3 Study Duration, Enrollment and Number of Subjects**

We anticipate that the entire study will last approximately 3 years. Each subject's participation will last approximately 3 hours and 45 minutes over approximately 2 weeks.

### **3.4 Study Population**

We will recruit subjects who meet the following criteria:

- 1) age 18-35 years
- 2) undergone unilateral ACLR within 5 years prior to participation
- 3) at least 6 months post-ACLR
- 4) no history of ACL graft rupture or revision surgery
- 5) no history of neurological disorder
- 6) no history of injury to either leg within 6 months prior to participation (other than the initial ACLR)
- 7) Knee Injury and Osteoarthritis Outcome Score (KOOS) self-report survey Pain subscale score > 53.1 and Symptom subscale score > 44.9
- 8) cleared by a physician for return to physical activity, and currently physically active, participating in at least 20 minutes of physical activity 3x per week.

Age will be restricted to 18-35 years as this age group is at the greatest risk of ACL injury but is unlikely to possess idiopathic/non-traumatic knee OA. The post-ACLR interval (6 months-5 years) will ensure that subjects are outside the acute inflammatory phase and reduce the likelihood that they have already developed post-traumatic knee OA. A history of graft rupture or bilateral ACLR may infer inadequate rehabilitation or flawed surgical procedures, and may alter the dependent variables. Neurological disorders, acute orthopaedic injuries, and high-level pain and symptoms in the ACLR limb may also influence the dependent variables. The criterion values for the KOOS subscale scores are based on reference values obtained from more than 4,000 individuals 1 and 2 years post-ACLR. Lastly, sedentary individuals may develop knee OA via other mechanisms (e.g. compromised waste-nutrient exchange) rather than the hypothesized loading mechanisms.

Though highly prevalent, not all individuals display quadriceps dysfunction following ACLR. We hypothesize that individuals who do not display quadriceps dysfunction are less likely to develop post-traumatic knee OA, and would receive limited benefits from vibratory stimuli. Self-report surveys, including the KOOS, will always be assessed first followed immediately by quadriceps function. In the event that subjects do not possess quadriceps dysfunction (i.e. CAR < 95%), they will be excluded from the investigation. These procedures will ensure that we enroll the target population.

## **4 STUDY PROCEDURES (what will be done)**

Subjects will report to the UNC Neuromuscular Research Laboratory for three separate sessions. During Session 1, subjects will complete the approved informed consent document, as well as the Self-Report Surveys, Gait Biomechanics Assessment, and Quadriceps Function Assessment described below. These procedures will be used to determine if subjects meet the inclusion criteria, familiarize the subject with the testing procedures, and establish parameters necessary for the subsequent testing sessions to expedite data collection. Upon reporting to the laboratory for Session 2, subjects will perform a 5 minute warm up on a stationary cycle ergometer at a self-selected pace to reduce the likelihood of injury. They will then be fitted with motion capture markers and electromyography (EMG) electrodes followed by the Gait Biomechanics and Quadriceps Function assessments. They will then perform the respective intervention to which they have been assigned, followed by post-test measures of the aforementioned assessments. Procedures for Session 3 will be identical with the exception that the Proprioception/Sensory Assessment described below will be performed prior to and following the interventions. Sessions 2 and 3 will be separated by 1-week washout periods, and the order of these sessions will be counterbalanced.

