### **6.2 Statistical Methods**

**Specific Aim 1: To determine the effects of WBV and LMV on quadriceps function, proprioception, and gait biomechanics in individuals with ACLR.**

Analyses for Aim 1 will be performed using pre-post change scores for quadriceps function, proprioception, and gait biomechanics as dependent variables in separate statistical models. Mean change scores will be compared across groups (WBV, LMV, and Control) via one-way analysis of covariance (ANCOVA). Dunnett's procedure will be used to evaluate each the least-squares means for each of the intervention arms (WBV and LMV) versus control in a relatively powerful manner while controlling the overall significance level at two-sided 0.05. The corresponding pre-test values for each dependent variable will be managed as a covariate in these models to increase precision of the treatment effects, as well as to account any random imbalances among the groups with respect to these pre-scores. Other covariates would include variables with random imbalances across the groups measured at the pre-test.

The number of individuals who display HST prior to and following the intervention (or control) will be compared via McNemar's test. This analysis produces a  $\chi^2$  statistic for paired samples (i.e., the proportion with HST at pre-test vs. post-test, separately for each group).

**Specific Aim 2: To compare the effects of WBV and LMV on quadriceps function, proprioception, and gait biomechanics in individuals with ACLR.**

Aim 2 will be evaluated using the statistical models described above for Aim 1, but with focus on the statistical contrast of WBV versus LMV. Specifically, the pre-post change scores for each dependent

variable, adjusted for covariates, will be tested for the pairwise comparison of WBV versus LMV at the two-sided 0.05 significance level.

**Specific Aim 3: To identify factors that predict the effects of LMV and WBV on quadriceps function, proprioception, and gait biomechanics in individuals with ACLR.**

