Aim 3 will be evaluated using multiple regression models. Pre-post change scores for each dependent variable will be included only for the WBV and LMV groups. We will then calculate simple correlations between these change scores and the pre-test values separately for quadriceps function, proprioception, and the KOOS. We hypothesize that individuals with greater quadriceps dysfunction and proprioceptive deficits combined with lower KOOS scores (i.e. greater pain, symptoms, etc.) will display greater improvements. Separately for each dependent variable, these variables will then be placed into a stepwise multiple regression model (starting with a forward selection step). In this way, the variable with the strongest relationship with the change score will be entered first, followed by the next strongest (after adjusting for the first), etc. The model selection will stop when no additional variables are identified to enter to leave the model at the 0.10 significance level. This less conservative significance level is selected to cast a wide net to include relevant candidate terms. Next, we will examine each of these terms, one-at-a-time, as an independent variable in another regression model where the change score is the dependent variable; an indicator term for the intervention (WBV vs. LMV) will also be included as an explanatory variable, as well as the interaction between the intervention indicator and the candidate term. The initial focus will be on the significance of the interaction term, as this will determine whether the effect of the candidate term is homogeneous (reflected by non-significance of the interaction at the 0.05 level) across the interventions, or not. If the test is non-significant, the interaction term will be removed and the model refitted; the candidate term is then assessed from this model regarding its ability to predict the homogeneous effect of LMV and WBV on the corresponding dependent variable. If the interaction test is instead statistically significant, then the interaction term is retained in the model, and statistical contrasts will be constructed to estimate and test the separate effects of the candidate term by intervention group.

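### With the order of Sessions 2 and 3 counterbalanced, about half of the vibrated participants have their only proprioception pre-test a week after a first exposure, and no model accounts for session order

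*Combined protocol and SAP*

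**What the plan says.** The trial has three parallel arms: "Stratified randomization into 3 groups of equal size (n = 25) will be performed using a computer generated randomization algorithm" (section 3.2). Section 4 describes three visits.

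- **Session 1** covers consent, "as well as the Self-Report Surveys, Gait Biomechanics Assessment, and Quadriceps Function Assessment described below". Proprioception is not in that list.
- **Session 2** has gait and quadriceps pre-tests, then: "They will then perform the respective intervention to which they have been assigned, followed by post-test measures of the aforementioned assessments".
- **Session 3** is described as the same as Session 2, except that "the Proprioception/Sensory Assessment described below will be performed prior to and following the interventions".
- **Order:** "Sessions 2 and 3 will be separated by 1-week washout periods, and the order of these sessions will be counterbalanced".

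In section 6.2, Aim 1 analyses pre-post change by ANCOVA, and the "pre-test values for each dependent variable will be managed as a covariate in these models". The only other covariates foreseen are variables found to be imbalanced at pre-test. Aim 3 begins with "simple correlations between these change scores and the pre-test values separately for quadriceps function, proprioception, and the KOOS" and passes these variables to stepwise regression. Session order appears in neither aim.

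Section 3.1, in contrast, says that the vibration groups get one session of vibration. The synopsis puts two testing sessions, about a week apart, in the intervention phase.

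**The concern.** Each participant gets the same intervention at both visits, so there is no treatment sequence to balance. Counterbalancing does, however, decide whether the proprioception pre-test comes before or after a first exposure. For one of the two orders it comes after, and there is no other proprioception measurement to fall back on. A pre-test that the assigned treatment may have shifted is no longer a clean baseline. It enters the change score, the covariate adjustment and the Aim 3 predictor set.

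The proprioception analysis also pools first-exposure and second-exposure responses with no term to separate them. Knee joint position sense is a listed efficacy evaluation in the synopsis, and section 13 plans one of three main manuscripts on somatosensory function. It is not the primary outcome: section 6.3 gives that place to quadriceps function.

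**Working it through.** **What the plan's figures cover.** The 25 per group rests on quadriceps effect sizes (section 6.3). The stated 13-26 per group reproduces with the one-sided normal formula n = 2(1.645 + 0.842)²/d² = 12.37/d²: d = 0.98 gives 12.9, so 13; d = 0.70 gives 25.2, so 26. The plan gives no effect size, SD or carry-over figure for proprioception, so what follows on bias is illustration.

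**Step 1: how many are affected.** There are 2 vibration arms × 25 = 50 participants. With a 1:1 order split (assumed), 50 × 1/2 = 25, or 12-13 per arm, have their proprioception pre-test after a first exposure. In the Control arm the same share have it after a first Control session.

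**Step 2: what carry-over would do.** Let δ be the true effect, c the share of it still present after one week, and b the within-arm slope of post-test on pre-test. With half of the arm exposed, the mean pre-test of a vibration arm shifts by cδ/2 relative to Control. The ANCOVA estimate is the difference in mean post-test minus b times the difference in mean pre-test. It is the same whether the outcome is the change score or the post-test.

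- *Capped response* (the second session brings the participant only to the full effect): the post-test difference is δ, so the estimate is δ(1 − bc/2).
- *Additive response* (the second session gives the same acute change on top of the residual): the post-test difference is δ + cδ/2, so the estimate is δ[1 + (1 − b)c/2].

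Take b ≈ 0.6 (assumed pre-post correlation with equal SDs):

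| c | Capped: 1 − 0.3c | Additive: 1 + 0.2c |
|---|---|---|
| 0 | 1.00 | 1.00 |
| 0.10 | 0.97 | 1.02 |
| 0.25 | 0.925 | 1.05 |
| 0.50 | 0.85 | 1.10 |

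Simulation at 25 per arm, with δ = 0.70 SD and correlation 0.6, gave about 4%, 7% and 15% shrinkage (capped) and about 2%, 6% and 11% inflation (additive). That agrees with the formulas up to simulation error and small changes in b. For the capped case with correlation 0.5 to 0.8, the factor at c = 0.5 was 0.88 to 0.80.

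**Step 3: chance imbalance in order.** Section 4 does not say that order is balanced within arm. If it were assigned by coin flip, two arms of 25 would differ by 5 or more in session order with probability 0.20. The effect is small: a 5/25 imbalance with an assumed 0.2 SD order shift moves a contrast by 0.2 × 0.2 = 0.04 SD.

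**Step 4: which visit supplies the other outcomes.** If Session 3 repeats the gait and quadriceps tests, there are two change scores per participant for those outcomes. Section 6.2 does not say which is analysed. If it is Session 2, participants who did Session 3 first have post-exposure gait and quadriceps pre-tests. Those who did Session 2 first then have a proprioception predictor measured after the change it is meant to predict. If it is Session 3, predictor and change come from one visit and the time order is correct.

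**The case against.** The strongest defence is the washout. The trial studies acute effects (section 6.1), and the only persistence evidence cited shows an effect lasting minutes, with testing to 30 minutes (section 1.4). If nothing remains after a week, the pre-test is as good as unexposed and there is no bias. This stands as a reason to expect little carry-over. It does not close the point: that evidence is quadriceps EMG after LMV in healthy people, and there is nothing for proprioception, for WBV or for this population.

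Three stronger readings are tempting, and the documents do not support them.

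- *The proprioception effect will be diluted.* This needs both carry-over and a capped second response. If responses add, the error runs the other way. The documents support neither model, and planning a washout is a safeguard, not evidence of carry-over.
- *Aim 3 uses predictors measured after the outcome.* This holds only for Session 2 change scores in participants who did Session 2 first, and the plan does not say that those data are used.
- *The counterbalancing should be deleted.* Balancing two different test batteries against visit order and practice is a legitimate aim. With the proprioception session always first, first-exposure quadriceps data would always come from the longer battery. If Session 3 replaces tests rather than adding them, all primary-outcome data would be second-exposure.

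It is also fair that order variance is minor. In simulation, order shifts of 0.1-0.3 SD left power at 0.84-0.85, against 0.848 without a shift.

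**Conclusion.** The structural point holds. On section 4 as written, about 25 of 50 vibrated participants have their only proprioception pre-test about a week after a first exposure, and session order is in no model. This assumes a 1:1 order split and that the intervention is given at both visits. Should the one-session statement in section 3.1 govern, the problem would disappear, so the two sections must be reconciled.

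The consequence is an unverified reliance on the washout, not a shown bias. The distortion is nil without carry-over and of unknown sign with it. In the illustrations, it is at most about 15% of the effect at 50% carry-over with correlation 0.6, and about 20% with correlation 0.8. A correction is worthwhile because it is almost free and because an unexposed baseline cannot be recovered after data collection.

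**What to change.** 1. Reconcile section 3.1 with section 4 on the number of vibration sessions each participant receives.
2. Block session order within each arm, so that each has a 12/13 split.
3. Add session order as a factor to the proprioception ANCOVA, and to the other models if data from both orders are used. A main effect of order does not by itself remove carry-over bias. Therefore add an order-by-group check and a sensitivity analysis restricted to participants whose proprioception session came first.
4. State which session supplies the gait and quadriceps change scores. In Aim 3, take the proprioception predictor and the change score from the same visit.

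**Cost.** One degree of freedom in the main model (two more in the three-arm interaction check), a blocked order list and a few sentences; no new visits or tests. The restricted analysis has only 12-13 per arm. Borrowing the quadriceps effect of 0.84, its power in a two-sided t-test at 0.05 would be about 50% to 54%, so it supports the main result and is not a test in its own right.

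**Optional, not required.** Running the proprioception session first for everyone would give an unexposed baseline throughout. Consider it only if Session 3 truly repeats all Session 2 tests and the longer battery does not delay the quadriceps post-test.
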